6.8 TREATMENT COMPLIANCE

Not applicable.

6.9 ANALYSIS OF ENDPOINTS

The primary objective is to assess the psychometric properties and performance of the PGI-S items.

The focus of the analyses will be to describe the responsiveness to change of the PGI-S items to the subjects' self-reported symptoms of PAH at the end of the activity and during recovery from the activity. The Sponsor will tabulate the relevant symptom scores and compute change from Baseline (pre-activity) scores for each item. Data may be displayed graphically and will be summarized overall and by cohort and sequence/period (as appropriate).

Additionally, for Cohort A, the sensitivity to a known inhaled treprostinil drug effect will be assessed. Tabulations will be made across sequences/periods for the PGI-S measurements with inhaled treprostinil to PGI-S measurements without inhaled treprostinil. Test-retest assessments for PGI-S measurements will be conducted for Cohort B.

Correlations between the 3 PGI-S questions and with Borg dyspnea scores, oxygen saturation, and HR will be assessed. Data for HR recovery at 1 minute after the ISWT will be examined in an exploratory fashion overall and as related to PGI-S measurements.

The onset and recovery profile for activity-induced symptoms will also be characterized.

6.10 HYPOTHESIS TESTING

Not applicable.

Summary statistics will be computed to characterize the difference between peak and trough conditions in Cohort A, correlations between conditions, variability measures, and sequence/period effects (as appropriate). Summary statistics will include the mean, N, standard deviation, median, mode, minimum, maximum, the 25th and 75th percentile values, and 95% confidence intervals for the mean and difference values.

6.11.4 *To Assess the Ability of the PGI-S Response Scale to Detect Resolution in Activity-induced Symptoms*

The analysis of PGI-S item-level data will assess the time to resolution of symptoms (return to baseline values) measured *after* completion of the ISWT (ie, change score ≤ 0) for PGI-S Overall PAH Symptoms, PGI-S Shortness of Breath, and PGI-S Physical Fatigue on Day 1. Summary statistics will include frequencies and percentages by protocol-specified evaluations, ie, 0 to 5 minutes, >5 to 10 minutes, etc, by cohort.

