4 SUBJECT ELIGIBILITY

4.1 INCLUSION CRITERIA

Subjects who meet the following criteria may be included in the study:

1. Subject voluntarily gives informed consent to participate in the study.
2. Males and females aged 18 years and above at the time of informed consent.
3. Established primary diagnosis of PAH that is either idiopathic or familial PAH (WHO Group 1), collagen vascular disease associated PAH, PAH associated with human immunodeficiency virus (HIV) infection, PAH induced by anorexigens/toxins, or PAH associated with repaired congenital systemic-to-pulmonary shunts (repaired ≥ 1 years).
4. Subject is deemed WHO Functional Class I, II, or III.
5. Subject has shortness of breath upon exertion (exhibits a ≥ 1 -point change in Borg dyspnea score) as assessed by the ISWT and a minimum completion of 3 shuttles (30 meters) of the ISWT. Subject may have other symptoms as well.
6. Subject is on stable dose of all FDA-approved PAH treatments (exceptions are anticoagulants and diuretics) for at least 60 days prior to Screening.
7. In the opinion of the Investigator, the subject can communicate effectively with study personnel, and is considered reliable, willing, and likely to be cooperative with protocol requirements.

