2.2 SECONDARY OBJECTIVES

The secondary objectives of this study are:

- To characterize the relationship of PGI-S questions with:
 - Borg dyspnea score

- Oxygen saturation
- Heart rate (HR)
- HR recovery at 1 minute after the Incremental Shuttle Walk Test (ISWT)
- To characterize the recovery profile for activity-induced symptoms.

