5.1 OBSERVATIONAL ENDPOINTS

5.1.1 *Patient Global Impression of Severity*

The primary objective is to characterize the psychometric properties and performance of the 3 PGI-S items, measuring overall PAH symptoms, shortness of breath, and physical fatigue during pre-ISWT, at the end of activity, and through recovery.

The focus of each item, separately, will be the subject's evaluation of:

1. Overall PAH Symptoms: [REDACTED]
2. Shortness of Breath: [REDACTED]
3. Physical Fatigue: [REDACTED]

Subjects will be asked to rate each item based on their level of symptom severity "at this moment" using a 5-point ordinal response scale (1=Not present, 2=Mild, 3=Moderate, 4=Severe, 5=Very severe). The timing of the assessments for Overall PAH Symptoms, Shortness of Breath, and Physical Fatigue scales will be at Screening/Baseline (-15 minutes and at 0 minutes

prior to activity-inducement of PAH symptoms), at completion of the ISWT, and every 1 minute for 5 minutes then every 5 minutes following completion of the ISWT during recovery. The average recovery time of symptoms is unknown but, based on clinician advice, it is expected that recovery should be within 15 to 20 minutes. Assessments for PGI-S will occur for 30 minutes following completion of the ISWT to ensure that the full recovery profile is captured across all subjects observed.

For each PGI-S item, a change from Baseline score will be calculated for the PGI-S items measured from the start of the activity-inducement of PAH symptoms.

5.1.2 *Modified Borg Dyspnea Score*

The Modified Borg Dyspnea score (see Section 9) will be completed by subjects as follows: Subjects will be asked to rate dyspnea “at this moment” on an 11-point numeric rating scale (0=Nothing at all, 10=Maximal) at Screening/Baseline (-15 minutes and at 0 minutes prior to activity-inducement of PAH symptoms) and at completion of the ISWT.

5.1.3 *Oxygen Saturation and Heart Rate*

Oxygen saturation and HR will be measured continuously throughout the observation period with measurements extracted and recorded into eCRFs at Screening/Baseline (-15 minutes and at 0 minutes prior to activity-inducement of PAH symptoms), each minute during the ISWT, at completion of the ISWT, and every 1 minute for 5 minutes then every 5 minutes following completion of ISWT during recovery. Key measurements used for analysis will be those that correspond to the measurement of the PGI-S and Borg Dyspnea scores.

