6 STATISTICAL METHODS

6.1 DATASETS FOR ANALYSES

This study has the following analysis populations:

- All Subjects (All): Subjects who consented to the study protocol.
- Full Analysis Set (FAS) Population: Subjects who enrolled in the study protocol (initiated Day 1 procedures). Tabulations for endpoint analyses will be conducted on this population.
- Per-Protocol (PPROT) Population: Subjects who completed the study protocol, do not have significant protocol deviations in the study, and were appropriately included to investigate the research hypotheses. The Sponsor will assess inclusion of this population at the time of database lock. Endpoint analyses may be conducted from this population if the population is applicable after Sponsor review.
- Safety Population: Subjects who initiated the ISWT at Screening.
- Psychometric Analysis Population (PAP): Subjects who completed the PGI-S items or Modified Borg Scale at any visit or time point.

Summary tables will be presented with the number and percentages of subjects overall and by cohort.

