6.13.5 Responsiveness to Change

It is important to provide evidence regarding the responsiveness of the PGI-S items—that is, their ability to detect change when change is expected. The responsiveness of the PGI-S items will be evaluated by computing effect-size estimates of change for each PGI-S item as the mean change from the first time point to the second time point divided by the standard deviation at the first time point. In addition, the observed score changes and associated t-tests (p-values) will be tabulated. Baseline (pre-ISWT -15 minutes and 0 minutes) to 0 minutes post-ISWT will be examined, as will 0 minutes post-ISWT to 30 minutes post-ISWT (end of recovery period).

Cohen (1992) provides a general rule of thumb for the interpretation of effect-size estimates: effect sizes of approximately 0.20 represent small effects, those of approximately 0.50 represent moderate effects, and those greater than approximately 0.80 represent large effects.

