11 LIST OF TABLES AND FIGURES

Table No.	Title	Population
14.1.1	Summary of Subject Accountability and Disposition	All
14.1.2	Summary of Analysis Populations	All
14.1.3	Summary of Demographic and Baseline Characteristics	All
14.1.4	Summary of Medical and Surgical History	All
14.1.5.1	Summary of Prior Medications	All
14.1.5.2	Summary of Concomitant Medications	All
14.1.6	Summary of Protocol Deviations	All
14.2.1.1	Summary of PGI-S Change from Baseline	All
14.2.1.2	Summary of PGI-S Change from Baseline	PPROT
14.2.1.3	Figures for PGI-S Change from Baseline	FAS
14.2.1.4	Figures for PGI-S Change from Baseline	PPROT
14.2.1.5	Summary of PGI-S Time to Recovery	FAS
14.2.1.6	Summary of PGI-S Time to Recovery	PPROT
14.2.2.1	Summary of Borg Change from Baseline	All
14.2.2.2	Summary of Borg Change from Baseline	PPROT
14.2.2.3	Summary of Pulse Oximetry and Heart Rate	All
14.2.2.4	Summary of Pulse Oximetry and Heart Rate	PPROT
14.2.2.5	Figures for Pulse Oximetry and Heart Rate	FAS
14.2.2.6	Summary of ISWT	All
14.2.3.1	PGI-S Response Frequency (%) Distributions	PAP
14.2.3.2	PGI-S Construct Validity Correlations	PAP
14.2.3.3	PGI-S Known-Groups ANOVAs	PAP
14.2.3.4	PGI-S Test-retest Reliability	PAP
14.2.3.5	PGI-S Responsiveness	PAP
14.3.1.1	Summary of Treatment-emergent Adverse Events by System Organ Class and Preferred Term in Decreasing Order	Safety
14.3.1.2	Summary of Treatment-emergent Adverse Events by Preferred Term in Decreasing Order	Safety
14.3.1.3	Summary of Serious Treatment-emergent Adverse Events by System Organ Class and Preferred Term in Decreasing Order	Safety
14.3.1.4	Summary of Treatment-emergent Adverse Events by Severity by System Organ Class and Preferred Term in Decreasing Order	Safety
14.3.1.5	Summary of Treatment-emergent Adverse Events Leading to Study Discontinuation by System Organ Class and Preferred Term in Decreasing Order	Safety

14.3.2.1	Listing of Deaths	Safety
14.3.2.2	Listing of Serious Adverse Events	Safety
14.3.3	Summary of Vital Signs	Safety

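### The time-to-resolution rule (change score ≤ 0) does not require a prior rise, so a walk with no PGI-S increase is counted as resolved at 0 to 5 minutes

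*SAP*

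**What the plan says.** SAP 6.11.4 assesses how long each PGI-S item takes to return to baseline on Day 1, measured after "completion of the ISWT (ie, change score ≤ 0) for PGI-S Overall PAH Symptoms", with the same rule for Shortness of Breath and Physical Fatigue. Results are reported as "frequencies and percentages by protocol-specified evaluations, ie, 0 to 5 minutes, >5 to 10 minutes, etc, by cohort".

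The rest of the plan bears on this as follows:

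- **Change score.** SAP 6.3.2 takes the post-baseline rating minus the average of the −15 and 0 minute ratings. SAP 6.3.1 allows a different baseline in recovery, with a footnote, but 6.11.4 does not name one.
- **Population.** SAP section 11 lists "Summary of PGI-S Time to Recovery" twice, on the FAS (14.2.1.5) and on the per-protocol set (14.2.1.6). SAP 6.1 describes the FAS as "Subjects who enrolled in the study protocol (initiated Day 1 procedures". The per-protocol set adds study completion, absence of significant deviations and appropriate inclusion.
- **Entry.** Protocol 4.1, criterion 5, asks for at least a 1-point "change in Borg dyspnea score) as assessed by the ISWT and a minimum completion of 3 shuttles (30 meters) of the ISWT". That is a Borg criterion, met at Screening.
- **Objective.** SAP 2.2 lists as a secondary objective "To characterize the recovery profile for activity-induced symptoms".

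**The concern.** Resolution has a meaning only for a walk that produced symptoms. The plan's words about returning to baseline imply a departure from it, but the operative rule is the inequality alone, and a walk that never left baseline satisfies it at once. Such walks are placed in the earliest bin and make recovery look faster than it was among walks that had something to recover from.

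The section is meant to show that the response scale can detect resolution. Under this rule an item that never responded to the walk would show 100% resolution at 0 to 5 minutes, so the least responsive item would look best.

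The table is also split by cohort. If the share of walks with no rise differs between cohorts, two cohorts with the same recovery among risers will appear to differ.

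**Working it through.** **What the rule does.** The plan states no figure for time to resolution, so there is none to reproduce. The rule can be applied to every possible flat pattern on the 1 to 5 scale: 25 pairs of baseline ratings times 5 constant post-walk ratings, 125 in all. For a pair with sum s, the post-walk ratings with change ≤ 0 number floor(s/2). Summing over s = 2 to 10 gives 1 + 2 + 6 + 8 + 15 + 12 + 12 + 8 + 5 = 69. All 69 fall in the 0 to 5 minute bin, whether or not the rating at completion is used, because the minute-1 rating already meets the rule. The only exception is a walk whose ratings through minute 5 are all missing.

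**Effect on the table.** Let p0 be the share of walks with no rise and q the share of rising walks resolved by 5 minutes.

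- Share shown at 0 to 5 minutes = p0 + (1 − p0)q
- Excess over q = p0(1 − q)

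Neither rate is in the documents. SAP 5.1.1 says "The average recovery time of symptoms is unknown" and cites clinician advice that recovery should come within 15 to 20 minutes, which does not fix q. The values below are assumptions. Each cell gives the share shown, with the excess in percentage points in brackets.

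| p0 | q = 20% | q = 40% | q = 60% |
|---|---|---|---|
| 5% | 24% (4) | 43% (3) | 62% (2) |
| 20% | 36% (16) | 52% (12) | 68% (8) |
| 40% | 52% (32) | 64% (24) | 76% (16) |

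**When it becomes material.** Taking 5 points as the mark, the excess passes it once p0 exceeds 0.05/(1 − q): 6.25%, 8.3% and 12.5% for q = 20%, 40% and 60%. With 36 evaluable subjects in equal cohorts (Protocol 5.2) there are 18 per cohort. Two Day 1 walks each make 36 walks. The thresholds are then 36 × 0.0625 = 2.25, 36 × 0.0833 = 3.0 and 36 × 0.125 = 4.5, so 3, 4 or 5 non-rising walks per item and cohort exceed the mark. This pools both periods, which 6.11.4 does not state.

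**Is such a p0 plausible?** As a rough guide only, take a normal change score with the planning SD of 1.3 (SAP section 4) and an assumed mean rise of 1 category. P(change ≤ 0) = Φ(−1/1.3) = 22%. Allowing for half-point or whole-point scoring it is Φ(−0.75/1.3) = 28% or Φ(−0.5/1.3) = 35%. Over assumed mean rises of 0.5 to 2.0 the range is 50% down to 6%.

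**Cohort contrast, on assumed values.** With q = 40% in both cohorts and p0 = 10% in one and 30% in the other, the table shows 0.10 + 0.90 × 0.40 = 46% against 0.30 + 0.70 × 0.40 = 58%.

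**Secondary point, the averaged baseline.** Ratings of 1 then 2 average 1.5. A subject back at the 0-minute rating of 2 has change 2 − 1.5 = +0.5 and is not counted as resolved; against the 0-minute rating the change is 0. This acts in the opposite direction. Its frequency is unknown and probably small.

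**The case against.** The strongest reply is that 6.11.4 defines the event and leaves the set of walks at risk open. Its title and its language of return presuppose induced symptoms. The FAS and per-protocol sets are defined for subjects and need not settle which walks count. SAP section 1 puts table layouts in separate mock-ups, which were not available and may restrict the denominator or add rows. That limits the finding to the SAP text. It does not rescue the text, which gives the inequality as the meaning of resolution and names no at-risk set.

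A share of all walks at or below baseline by 5 minutes is also a legitimate description. So it is, but under that label, not as time to resolution.

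Walks unresolved at 30 minutes could be read as the remainder from 100%. That is partly right. However, SAP 6.4.1 does not impute missing data, so the remainder would mix unresolved walks with missing ratings.

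The size is assumed, and the upper end is less likely for Shortness of Breath, given the Borg entry criterion and the instruction to walk until too breathless or unable to keep pace. This stands. It bears less on Physical Fatigue and guarantees no PGI-S rise on Day 1 for any item.

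Other outputs would expose an item that does not move. SAP 6.11.1 graphs individual data and gives quartiles of the pre-post difference; a 25th percentile at or below 0 would show that about a quarter of walks or more did not rise. SAP 6.13.2 gives the response distributions at 0 minutes post-ISWT. In SAP 6.13.5, "Baseline (pre-ISWT -15 minutes and 0 minutes) to 0 minutes post-ISWT will be examined, as will 0 minutes post-ISWT to 30 minutes post-ISWT". These limit the harm but do not correct the time-to-resolution table.

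**Conclusion.** The concern holds for the SAP as written. The rule counts walks with no PGI-S increase as early resolutions, and no other provision removes them. The mechanism is certain from the text. The size depends on two rates the documents do not give: 2 to 32 points over the assumed grid, and small if fewer than about 3 to 5 of 36 walks per cohort fail to rise on an item.

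The table is descriptive, no hypothesis test rests on it and the raw scores remain. It should nevertheless be fixed, because this is the section that tabulates time to resolution for a stated secondary objective, and the rule flatters an unresponsive item. The baseline question is a lesser matter.

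**What to change.** In SAP 6.11.4:

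1. Compute time to resolution only for walks whose rating rose above the recovery baseline: change > 0 at completion, or at a stated early post-walk rating so that a delayed peak is not missed. The 1-category change that SAP 6.11.1 treats as meaningful can serve as a sensitivity analysis.
2. Report walks with no rise and walks unresolved at 30 minutes in separate rows, by item and cohort.
3. State which baseline applies in recovery, as SAP 6.3.1 permits, so that averaging alone does not leave a subject who is back at the 0-minute rating at +0.5.

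The cost is SAP wording and a little programming, with no new data. The drawbacks are smaller denominators that differ by item, and more noise if a single 0-minute rating replaces the average of two. Requiring the rise at completion alone would put delayed peaks in the no-rise row, so the rating used must be written down. This is best settled before results are tabulated, since SAP 7.4 allows the data to be evaluated at any time.

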6.12 SUPPORTIVE ANALYSES

6.12.1 *Borg Dyspnea Score*

Summary statistics will be computed to characterize average change and variability overall and by cohort and sequence/period (as appropriate). The pre-ISWT (average of -15 and 0 minutes), post-ISWT at each time point, and pre-post difference for Borg Dyspnea score will be provided. Summary statistics will include the mean, N, standard deviation, median, mode, minimum, maximum, the 25th and 75th percentile values, and 95% confidence intervals for the mean and difference values.

6.12.2 *Pulse Oximetry and Heart Rate*

Summary statistics will be computed to characterize average change and variability overall and by cohort and sequence/period (as appropriate). The pre-ISWT (average of -15 and 0 minutes), post-ISWT at each time point, and pre-post difference for oxygenation and HR will be provided. Summary statistics will include the mean, N, standard deviation, median, mode, minimum, maximum, the 25th and 75th percentile values, and 95% confidence intervals for the mean and difference values.

6.12.3 *ISWT*

Tabulations will be provided by cohort and sequence/period (as appropriate) for the total number of shuttles completed, total distance walked (meters), use of oxygen during ISWT (Yes, No), reason for ISWT ending (Shortness of breath, Physical fatigue, Chest pain, Other), and time since most recent dose of PAH medication (Start time of ISWT - Time of most recent dose of PAH medication).

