3.3.2 Safety

Overall safety during the conduct of the study will be assessed on the following parameters: AEs, vital sign measurements, concomitant medications, and oxygenation.

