3.3.2.3 Oxygenation (Pulse Oximetry)

Pulse oximetry will be performed from the beginning of pre-ISWT (15 minutes prior to the ISWT) and will be continuous through the end of recovery. Pulse oximetry will include the collection of saturation of peripheral capillary oxygenation (SpO₂) and HR. The SpO₂ and HR measurements obtained at -15 and 0 minutes (prior to activity), every minute during the ISWT, every minute for the first 5 minutes of the recovery, followed by every 5 minutes for the remainder of the 30-minute recovery, will be recorded in the subject's source documents and electronic Case Report Form (eCRF).

A specific pulse oximeter model will be recommended by the Sponsor and the site will purchase and provide the Sponsor an invoice for reimbursement. In the event a pulse oximeter cannot be used (ie, subject has known issues with obtaining accurate readings from a finger probe, etc), an alternative device may be used with prior Sponsor approval, so long as the same device is used throughout the study.

3.3.2.4 *Adverse Events*

Adverse events will be recorded throughout the course of the study from the time of informed consent until the time a subject discontinues or subject completes the study. Each subject will be questioned for AEs at each study visit. Subjects will also be instructed to voluntarily report all AEs throughout the study.

All AEs should be followed until resolution (or return to normal or baseline values), until they are judged by the Investigator to no longer be clinically significant, or for at least 7 days if the AE extends beyond the end of study assessments. All AEs meeting criteria for a serious adverse event (SAE) should be followed until resolution, death, or until the subject is lost to follow-up, even if they are ongoing more than 7 days after study completion. All AEs/SAEs that occur while the subject is in the study will be recorded as instructed in this protocol.

Section 9 and Appendix 15.4 provide definitions and guidelines for recording AEs, respectively.

3.3.3 *Concomitant Medications*

All concomitant medications taken throughout the course of the study, including those taken for AEs, should be recorded in the subject's source documents and captured in the eCRF as required.

3.3.4 *Assessment of PGI-S Questions and Borg Dyspnea Scores*

3.3.4.1 *Incremental Shuttle Walk Test*

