10.3.3 Safety Analyses

Safety will be evaluated on AEs, vital signs, and oxygenation. All AEs as recorded by the Investigators will be assigned a MedDRA Preferred Term and System Organ Class by the Sponsor for reporting purposes. The summary of AEs will include the number and percentage of subjects, as well as the number of events reported for each Preferred Term. No inferential analyses are planned for the AEs.

Data collected at pre-ISWT will serve as baseline values for the evaluation of data collected during ISWT and recovery. Summary statistics will be calculated for measured values and changes from baseline values. No inferential analyses are planned on these safety endpoints.

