7 ANALYSIS OF SAFETY

The safety assessments will consist of AEs including serious adverse events (SAEs), and vital signs.

All safety analyses will be based on the Safety Population. No formal inferential testing will be reported for routine safety analyses.

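### The protocol makes oxygenation during the walk a safety evaluation; the SAP treats oximetry as supportive and commits to no summary of the in-walk SpO2 and HR readings

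*SAP*

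**What the plan says.** Protocol 3.3.2 states: "Overall safety during the conduct of the study will be assessed on the following parameters: AEs, vital sign measurements, concomitant medications, and oxygenation". The analysis section, 10.3.3, repeats it: "Safety will be evaluated on AEs, vital signs, and oxygenation". It then sets the comparison, "Data collected at pre-ISWT will serve as baseline values for the evaluation of data collected during ISWT and recovery", and the output, "Summary statistics will be calculated for measured values and changes from baseline values". Under Protocol 3.3.2.3, SpO2 and HR go into the eCRF before the walk and then "every minute during the ISWT, every minute for the first 5 minutes of the recovery", with five-minute readings to the end of the 30-minute recovery. Protocol 2.3, however, lists only adverse events and vital signs as safety objectives.

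The SAP takes the narrower list. Section 7 reads: "The safety assessments will consist of AEs including serious adverse events (SAEs), and vital signs". Sections 2.3 and 5.2 agree with it, and 7.3 limits vital signs to SBP and DBP. Oximetry is placed under observational endpoints and supportive analyses. SAP 5.1.3 acknowledges that readings are taken each minute of the walk, but says: "Key measurements used for analysis will be those that correspond to the measurement of the PGI-S and Borg Dyspnea scores". SAP 6.12.2 describes the summary as the average of the two pre-walk values, followed by "post-ISWT at each time point, and pre-post difference for oxygenation and HR will be provided". The Section 11 list has three oximetry outputs: Table 14.2.2.3 (All), Table 14.2.2.4 (PPROT) and the figures in 14.2.2.5 (FAS). None is in the 14.3 safety series.

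**The concern.** SpO2 and HR are the only physiological measurements taken while the subject is exerting. Blood pressure is measured only at the beginning and end of each visit. Appendix 15.2 describes the walk as maximal and progressive, and each enrolled subject is due to do it three times. If the SAP is followed as written, the evaluation of in-walk data promised in Protocol 10.3.3 need not appear in the report, although sites are asked to record those data every minute. A subject whose SpO2 falls during the walk and has partly recovered by the first summarised reading would not be shown at his or her lowest value.

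The change is also unmarked. Protocol Section 10 says that changes of statistical method will be documented in the SAP. SAP Section 1 says that it supersedes the protocol's statistical section, but no part of the SAP identifies this departure.

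**Working it through.** There is no planned figure to reproduce. The check compares the texts and counts scheduled readings.

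**Which data Protocol 10.3.3 means by data collected during the walk.** The safety measures named there are adverse events, vital signs and oxygenation. Vital signs are SBP and DBP (Protocol 3.3.2.2) and are not taken during the walk. Of the measurements that have a pre-walk baseline value, only those from the oximeter are recorded during it.

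**Whether the SAP text covers them.**
- The safety sections (2.3, 5.2, 7, 7.3) do not mention oximetry.
- The key measurements in 5.1.3 are tied to PGI-S and Borg times. PGI-S is given before the walk, at its end and in recovery; Borg is given before the walk and at its end. Neither is given during the walk.
- SAP 6.12.2 names the pre-walk average, post-walk time points and the pre-post difference. It names no during-walk value and no nadir.

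**Count of SpO2/HR readings per walk.**
- Before the walk: 2 (at -15 and 0 minutes).
- At completion: 1 (listed in SAP 5.1.3; not listed separately in Protocol 3.3.2.3).
- Recovery: 10 (at 1, 2, 3, 4, 5, 10, 15, 20, 25 and 30 minutes).
- Covered by the 6.12.2 wording: 2 + 1 + 10 = 13.
- During a walk of k whole minutes: k. If the last coincides with completion, k - 1 are not covered.

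The shortest walk that meets the screening criterion is 3 shuttles at 20 seconds each (Appendix 15.2): 3 x 20 = 60 seconds, so k = 1. The documents give no expected walk length. The values of 3, 5 and 8 minutes below are assumptions, and the last column takes 40 subjects x 3 walks = 120 walks.

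| Walk (min) | In-walk readings, k | Not covered, k - 1 | Not covered over 120 walks |
|---|---|---|---|
| 1 | 1 | 0 | 0 |
| 3 | 3 | 2 | 240 |
| 5 | 5 | 4 | 480 |
| 8 | 8 | 7 | 840 |

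If no in-walk reading coincides with a completion reading, all k are left out. That is 3 to 8 per walk for the 3- to 8-minute range, or 120 x 3 = 360 to 120 x 8 = 960 in all.

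**The case against.** The case on the other side has several parts, and much of it stands.

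- **The SAP matches the protocol's stated objectives.** Protocol 2.3 and the synopsis omit oxygenation from safety, and oxygen saturation appears as a secondary objective through its relationship with PGI-S. This is correct, so the protocol contradicts itself and the fault is not the SAP's alone. It does not remove the explicit commitment in 10.3.3.
- **Oximetry is still analysed.** A reader might infer that desaturation disappears from the report, or that a pooled post-walk mean hides individual subjects. The documents do not support that. SAP 6.12.2 summarises each post-walk time point separately, with minimum, maximum and quartiles, so the lowest value at each of those times is visible.
- **The population is adequate.** A reader might infer from the FAS figures that screen failures who walked are left out. Table 14.2.2.3 is on All subjects, meaning everyone who consented, and that includes the Safety Population.
- **A completion reading is listed in SAP 5.1.3.** Because the test gets harder towards its end, that reading would be taken close to the highest workload. A reader might want to state how much of an end-walk fall has gone by the first summarised value. The documents give no recovery rate for SpO2, so no such percentage can be supported.
- **The shells may include in-walk values.** The SAP keeps its mock-ups in a separate document, 5.1.3 speaks of key measurements rather than the only ones, and Protocol 10.3 and 10.6 promise tables and listings of the collected data. It therefore cannot be said that in-walk readings will appear nowhere, only that the SAP text does not commit to them.
- **Other walk information is tabulated.** SAP 6.12.3 covers the reason for stopping, including chest pain, and oxygen use. A reader might infer that safety would rest on adverse events and blood pressure alone, which goes too far.

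**Conclusion.** The point holds as a gap between the protocol's safety analysis section and the SAP. Oxygenation is a safety measure in Protocol 3.3.2 and 10.3.3, is absent from Protocol 2.3, and is absent from every safety section of the SAP. No summary described in the SAP text covers the readings taken during the walk or each subject's lowest in-walk SpO2, and the SAP does not document the departure.

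The size is modest and depends on walk length, which the documents do not give. The loss may be nil for a one-minute walk. It is about 2 to 7 readings per walk for assumed walks of 3 to 8 minutes when the last reading coincides with completion. These counts show how much recorded information is left unsummarised; they do not measure an effect on any conclusion. The primary PGI-S analysis is not affected. The change should be made, because a stated safety evaluation would otherwise be left out although its data are in hand.

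**What to change.** 1. Reconcile Protocol 2.3 with 3.3.2 and 10.3.3 on whether oxygenation is a safety measure, and record the resolution in the SAP.
2. Add oxygenation to SAP 5.2 and 7.
3. Extend SAP 6.12.2 to during-walk SpO2 and HR and their change from the pre-walk average.
4. Add one table to the 14.3 series on the Safety Population. For each walk (Screening, Period 1, Period 2) it would give the distribution of each subject's lowest SpO2 and highest HR between the start of the walk and the end of recovery, with the change from the pre-walk average, overall and by cohort. A split by supplemental oxygen use is optional.

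Protocol 10.3.3 promises only measured values and changes from baseline. The lowest and highest values are a compact way to deliver that when walks differ in length. If the sponsor prefers to leave in-walk data out, the SAP should say so and give the reason.

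The cost is SAP wording, a correction to the protocol text and one extra table from data already in the eCRF. Subjects and sites have nothing further to do, and no clinical threshold is introduced.
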